9.4.1 Overall description of the databases

9.4.1.1 Denmark: Danish National Registers

Danish National Registers have a 100% coverage of the country (around 5.8 million individuals). In general, the healthcare registers at the Danish Health Data Authority are updated monthly with a lag time of approximately 2 months. However, the study requires linkage to socio-economic registers, which are stored at Statistics Denmark and updated annually (after the end of December). The lag time to access this linked data varies from 3 to 15 months.

- **The Danish Civil Registration System**

The Danish Civil Registration System or Central Person Register (CPR) is operated by the Danish Ministry of the Interior. The Danish Civil Registration System was introduced in 1968 and contains information on demographics (age, sex, geographical region), migration and vital statistics data (date of birth and date of death) for all Danish residents. Every individual in Denmark is provided with a unique civil registration number (CPR number) at birth or upon immigration which allows for follow-up until death or emigration. The CPR number forms the basis for the precise, deterministic linkage of individual-level data between all patient-level registers and databases in Denmark, allowing the creation of a study database with individual-level data.

- **The National Health Insurance Service Register**

The National Health Insurance Service Register (*Sygesikringsregisteret* [NHISR]) records information on services supported by public health insurance and provided by general practitioners and specialists in private practice outside the secondary setting at hospitals. Information on the weekly invoicing of the costs covered by the public health insurance is included in the register. However, individual diagnoses and treatment information are not available (available in other registers). Data is available from 1990 onwards.

- **The Danish Register of Medicinal Product Statistics**

The Danish Register of Medicinal Product Statistics (*Lægemiddelstatistikregisteret* [RMPS]) holds patient-level data on all prescription drugs dispensed via community pharmacies. The register contains information on the date of purchase, item number, product name, ATC code,

strength per unit, quantity of the WHO's defined daily doses (DDD) per package and number of packages filled. Data are available from 1995 onwards. Since April 2004, information on the medical indication for a prescription and the daily prescribed dose by the prescribing physician is also available. However, the completeness and validity of these fields (medical indication and daily prescribed dose) are affected by the consideration that these data elements are not compulsory.

- **The Danish National Hospital Medication Register**

The Danish National Hospital Medication Register (Sygehusmedicinregisteret [SMR]) contains information on drugs administered to patients while admitted to hospital or during outpatient visits. It contains the date and time of drug administration, the dose administered via number of units and strength per unit, product name, ATC code, and department information. Thus, this register complements the RMPS. Data have been captured since May 2018 and were made available for research in 2022. As this is a new register, data may not be complete from the early years (may have some missingness).

- **The Danish National Patient Register**

The Danish National Patient Register (Danish NPR) is managed by the Danish Health Data Authority. It was established in 1977 and is considered to have a high degree of completeness and validity. It covers patients admitted to hospitals, emergency rooms, and specialty outpatient clinics (secondary care). Since 2007 the register has included information on all patients in Danish hospitals including private hospitals. However, reporting from private hospitals and clinics are not considered complete.

The Danish NPR register includes the following information: CPR number, local municipality, admission and discharge information, the date of any incidents over the course of an illness, diagnosis (Danish adaption of the ICD-10), examinations and treatment information - including surgery coded with Danish version of the Nordic Medico-Statistical Committee Classification of Surgical Procedures (Nordisk Medicinal-Statistisk Komité [NOMESCO]) codes, as well as supplementary information regarding births.

- **The Register of Laboratory Results for Research**

Information on laboratory tests at the country's large clinical biochemical and clinical immunological laboratories is collected in the National Laboratory Database daily. Tests performed in general practice and sent to a hospital laboratory for analysis are also included. This information is transferred to the Register of Laboratory Results for Research (RLRR). If a patient, has proactively denied consent to exchange lab results, then the results are not transferred to the RLRR. Two types of tests are included: a) analysis of blood, urine, joint fluids and spinal fluids for the purpose of preventing, diagnosing and controlling the treatment of human diseases; b) blood type determination and examination of blood e.g., pregnancy, immune disorders and certain infections. The register contains information on type of test, value, unit and date of sampling. Data from the five regions in Denmark has gradually been included in the register since late 2013. In addition, some historical data from before 2013 has also been transferred to the register.

Completeness is not reported but expected to be high. The RLRR is estimated to have reached 100% coverage by 2020. Only laboratory tests encoded with Nomenclature for Property and Unit (NPU) terminology are transferred from National Laboratory Database to the RLRR (currently approximately 95% of all laboratory tests). RLRR is updated weekly from the National Laboratory Database.

- **The Danish Medical Birth Registry (MBR)**

The Danish Medical Birth Registry (MBR) contains data on all live and stillbirths in Denmark since 1973. The registry contains high validity data on the actual birth, the outcome of the birth and whether there were complications during labour. The registry also includes information about the parents, including their municipality of residence, and their civil status and CPR numbers.

The MBR consists of a main table with index pregnancy (one line for each infant in the same pregnancy) as the key identifier and information on the identity on both parents by CPR number, diagnosis (ICD-10 codes) and possible complications, potential risk factors and number of prenatal visits. Any congenital abnormalities are retrospectively added to the table if identified within the first year of life. All subsequent health events reported by diagnoses and surgical interventions can be found in the NPR. All deaths of mother or infant within the first 365 days after delivery are registered including the age in days when the infant died.

- **The Danish Cause of Death Register (CDR)**

The Danish Cause of Death Register (CDR) contains information on date and cause of death. The information from the death certificate, including place of death, information about any autopsy, and municipality of residence is transferred to the CDR. Date of death is available from 1970 onwards. The register is updated once a year after end of December with a lag of approximately 13 months.

- **The Socio-economic registers at Statistics Denmark**

The Socio-economic registers cover a wide range of information on residents in Denmark. These include annual income by individual or family, highest achieved education, occupation, proportion of time outside employment due to sick leave etc., and information on individuals receiving different types of disability aid. Socio-economic registers at Statistics Denmark are updated annually, typically after end of December.

Study-specific data availability

The estimated annual number of pregnancies in women with SLE eligible for the MCM analysis and the select pregnancy loss outcomes analysis is 12 and 16, respectively (see Section 9.5.1 and Table 9).

Mother-offspring linkage is available since 1973, and all live births and stillbirths after 22 weeks of gestational age can be linked. This linkage is achieved using a deterministic approach.

Anifrolumab received marketing authorisation in Denmark in February 2022 and had a market launch in March 2022 (Table 4). It is provided to patients without any additional out of pocket costs. In Denmark, it is assumed that anifrolumab would be captured in SMR as it is administered at the hospital and administration of belimumab was captured in the registry.

Information on drugs dispensed through retail pharmacies (captured in the RMPS since 1995), drugs prescribed in hospital or in other institutional care (captured in the RMPS) and drugs administered in hospital (captured in the SMR since 2018) are available. ATC codes and Danish brand names enable the distinction between biologics.

All study outcomes of interest are available or partially available (Table 16), as well as maternal characteristics, other baseline characteristics and covariates (Table 17).

9.4.1.2 Finland

- **The Finnish Population Information System**

Every permanent resident of Finland (resident for at least one year) has a unique personal identity number (PIN). All national registers described below, record information using this unique number. This enables linkage of the different registers when permitted by patient consent or local regulation. The PIN is assigned by the Finnish Population Information System which is maintained by the Digital and Population Data Services Agency. The registry collects basic demographic information (age, sex, area of residence, date of death), sociodemographic characteristics, and migration. The registry data has been saved in an electronic format since 1971. Monthly updates are available, and the lag time is one month.

- **The Care Register for Health Care**

The register holder of the Care Register for Health Care (HILMO) is the Finnish Institute for Health and Welfare (THL). The data are available from 1994. HILMO contains data on both in- and outpatient secondary care. It has information on hospitalisation duration, diagnoses (ICD-10 codes), medical procedures, emergency room visits, and type of admission. HILMO also has data on day surgeries, patients discharged from inpatient care, number of patients in inpatient care in health centres and hospitals. However, there is no data available on hospital administered medication, which is captured in the electronic medical records. The reporting delay time is nine months. Therefore, the data from a given year is released for research in September of the following year.

- **The Register of Primary Health Care Visits**

The register holder of the Register of Primary Health Care Visits (AvoHILMO) is THL. The data are available from 2011 and occupational health and private sector were added in 2019. This register includes data from healthcare centres and institutions providing primary healthcare. Data on the time and place of the primary healthcare visits, reason for visit/diagnose (ICP-2 codes) and

procedures are recoded. The reporting delay time is nine months. Therefore, the data from a given year is released for research in September of the following year.

- **The Finnish National MBR**

Finnish national MBR is managed by THL and has data since 1987. The register contains data on all birth events, both live and stillborn in Finland with birth weight of at least 500 grams and gestational age of at least 22 + 0 weeks. Information on the mother, the infant and the course of pregnancy is also collected e.g., maternal diagnoses (ICD-10 codes), details of parturition, previous pregnancies and deliveries, infants' weight and height. Data on infants is collected until day seven. Since 2004, there is also a data file on small preterm infants that contains additional information of all live births in Finland with a birth weight of less than 1501 grams or gestational age less than 32 + 0 weeks. Data is collected to this data file until infant's age corresponds to 42 weeks' gestation. The registry has a lag time of around six months and new data is released annually in the summer.

- **The Register of CMs**

Register of CMs is managed by THL and has data since 1963. The register contains data on children who have been diagnosed with at least one major congenital chromosomal or structural anomalies. There is also data on other congenital anomalies such as congenital hypothyroidism and teratomas, detected or suspected in stillborn and live born infants and foetuses. Data on autopsy and other examinations are collected as well. Anomalies are recorded in accordance with the European network of population-based registries for the epidemiological surveillance of congenital anomalies (EUROCAT) guidance and ICD-10 codes. The congenital anomalies are recorded and followed during the first year of the child. The current lag time is three years, but the data holders have plans to reduce the lag time to two years.

- **The Register on Induced Abortions**

Register on Induced Abortions is managed by THL and has data since 1983. Data on all legally done induced abortions in Finland is collected. Healthcare units performing the procedures are mandated by law to report abortions. The variables recorded include grounds for the induced abortion, duration of pregnancy and method of termination and other practices. The register also collects data on the mother, such as number of previous pregnancies and method of contraception. The data from the previous year is available in November-December of the following year.

- **The Cause of Death Register**

The Cause of Death Register is managed by the Statistics Finland since 1971. It contains data on demographics, cause of death (ICD-10 codes) and time of death of all permanent residents in Finland. The complete data is collected from death certificates and the data from the previous year is available in January next year. The date of death is available earlier with a 5-month lag time.

- **The Prescription registers**

In Finland, there are 2 different prescription registers, the traditional prescription register and the e-prescription register. The traditional prescription register is managed by the Social Insurance Institute and has data since 1994. It covers only dispensed, reimbursed drugs. The e-prescription register is also held by Social Insurance Institute but managed by THL. The e-prescription register was founded in 2010 and electronic prescriptions became mandatory for all healthcare sectors in 2017. It covers all dispensed prescribed drugs (reimbursed and non-reimbursed). The variables include e.g., date of purchase and trade name, ATC code. Strength and package size of the drug product can be requested from the e-register.

- **The Finnish Electronic Medical Records**

Finnish Electronic Medical Records (EMRs) contain most of the specialist health care in their region. The research data is obtained from the hospitals' electronic patient records by using extraction of structured data and/or text mining. Start date for data collection varies between wellbeing services counties. The three biggest districts are Hospital District of Helsinki and Uusimaa (1,7 million residents in this region), Wellbeing services county of Pirkanmaa (500,000 residents), and Wellbeing services county of Southwest Finland (almost 500,000 residents). The Hospital District of Helsinki and Uusimaa is responsible for arranging secondary care in the Uusimaa region. Variables that are recorded in the hospital districts' EMR depends on which county is selected. Most of them include diagnosis, procedures, clinical notes, laboratory test results and hospital administered medication. Data lag time depends on the county which needs to be selected for the studies. EMR data is linkable to other Finnish data sources and can be applied for with the same data permit as other data sources.

- **Statistics Finland**

Statistics Finland collects demographic, socioeconomic, including educational level data of the Finnish population.

Study-specific data availability

The estimated annual number of pregnancies in women with SLE eligible for the MCM analysis and the select pregnancy loss outcomes analysis is 10 and 12, respectively (see Section 9.5.1 and Table 9).

Mother-offspring linkage is available since 1987, and all live births and stillbirths after 22 weeks of gestational age or with a birth weight over 500g can be linked. This linkage is achieved using a deterministic approach.

Anifrolumab received marketing authorisation in Finland in February 2022 but has not yet had a market launch. Finland's wellbeing counties have their own or a combined procurement agreement for hospital administered drugs. In this procurement agreement, it is decided which specific products will be used for that specific procurement period. If the drug (e.g., anifrolumab) is listed in the procurement agreement, it will be provided to patients without any additional out of pocket costs.

In Finland, information on drugs prescribed in hospital or in other institutional care and drugs administered in hospital or in other institutional care are available with possible unavailability in case of small patient counts (<5). In Finland, prescriptions and dispensing of oral and subcutaneous (SC) biologics are available from prescription registers, hospital administered medication, including anifrolumab, are available from EMRs. ATC codes will allow the distinction between biologics.

In Finland, all study outcomes of interest are available or partially available (Table 16), as well as maternal characteristics, other baseline characteristics and covariates (Table 17).

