9.2 Setting

A total of 6 large longitudinal patient-level data sources have been selected for this study, representing 5 countries: Denmark, Finland, France, Germany, and USA.

The included data sources are:

- Danish national health and socioeconomic registries (Denmark)
- Finnish national health and socioeconomic registries (Finland)
- National Health Data System (SNDS) (France)
- Rheuma-Kindwunsch und Schwangerschaft (RHEKISS) (Germany)
- Carelon Research (formerly known as Health Core Integrated Research Database - HIRD) (USA)
- Optum DAPI (USA)

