In DAPI, all study outcomes of interest are available or partially available (Table 16), as well as maternal characteristics, other baseline characteristics and covariates (Table 17).

Table 8: Summary of data sources and countries for this study

Country	Start of data availability	Coverage	Number of pregnancies in women with moderate to severe SLE per year ¹	Data lag (months)	Availability of exposure		Availability of outcomes				Rationale for the decision
					Anifrolumab ²	SOC	CM ³	Adverse pregnancy outcomes ⁴	Adverse birth outcomes ⁵	Infant growth outcome	
Denmark (National Registers)	Between 1970 and 2018 ⁶	100%	20	2-13	Available	Available	Available	Available	Available	Partial: - Length and weight are captured in the Children Database - No data on development available except for specific diagnoses	- Ability to capture anifrolumab exposure and primary outcomes
Finland (National Registers)	Between 1961 and 2019 ⁶	100%	16	1-24	Available	Available	Available	Partial: - Infections requiring hospitalisation during pregnancy	Available	Partial: - Height and weight might be available from HILMO and AvoHILMO	- Ability to capture anifrolumab exposure and primary outcomes
France (SNDS)	2008 (DCIR) 2006 (PMSI)	98.9%	263	12	Partial: - Only pen formulation of Belimumab delivered in retail pharmacies are captured. - Only hospital administered drugs listed as high-cost drugs are captured	Partial: - Vocosporin and mepacrine not available - Only hospital administered drugs listed as high-cost drugs are captured	Available	Partial: - Spontaneous abortion - Elective termination of pregnancy	Available	Partial: - Data on infant development is not available	- Ability to capture anifrolumab exposure (if included in the list of high-cost drugs) and primary outcomes ⁷
Germany (RHEKISS)	2015	NA ⁸	25	No	Available	Available	Available	Available	Available	Available	- Ability to capture anifrolumab exposure and primary outcomes

Country	Start of data availability	Coverage	Number of pregnancies in women with moderate to severe SLE per year ¹	Data lag (months)	Availability of exposure		Availability of outcomes				Rationale for the decision
					Anifrolumab ²	SOC	CM ³	Adverse pregnancy outcomes ⁴	Adverse birth outcomes ⁵	Infant growth outcome	
USA (Carelon Research)	2006	7% ⁹	225	3	Available	Available	Available	Available	Available	Available	- Ability to capture anifrolumab exposure and primary outcomes - Number of pregnancies captured

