9.5.1.2 Assumptions on data sources and number of pregnancies in SLE patients

To assess the anticipated study size in each data source, the total number of pregnancies in women with SLE were estimated in the feasibility assessment. Three data sources (Carelon Research, DAPI and RHEKISS) provided estimates for the annual number of pregnancies in women with SLE. For the data sources that did not provide estimates in feasibility assessments (Denmark, Finland, France), an estimate for the annual number of pregnancies in women with SLE was computed using the following parameters and assumptions:

- a) Latest available data on annual live births in the respective country of the data source (obtained from official statistical offices (42, 83));
- b) Data source coverage: Proportion of the country's total population covered by the data source (information obtained from the data sources during feasibility assessment);
- c) Proportion of live births occurring in SLE women among all live births. This information was only available for the USA, Denmark, and Sweden. Final estimates were obtained through different methods:
 - Denmark: average proportion from the Nordic countries (i.e., Denmark (58) and Sweden (94))
 - Finland: average proportion from the Nordic countries (i.e., Denmark (58) and Sweden (94))
 - France: average proportion from USA (21) Denmark (58) and Sweden (94);
- d) Proportion of non-live births in SLE pregnancies. According to a literature review, 20% of SLE pregnancies result in non-live births (22, 70, 82, 93, 103, 113). This proportion was used for all countries.

Based on the parameters and assumptions above, the following calculations were made for the data sources (Denmark, Finland and France):

1. The number of live births in SLE women captured by the data source was calculated as the number of annual live births in the country (parameter a) multiplied by the data source

coverage (parameter b) multiplied by the proportion of live births that occur in SLE women (parameter c);

2. The number of pregnancies in SLE women captured by the data sources was calculated as the number of live births in SLE women (step 1) divided by 0.80, as 80% (obtained from parameter d) of SLE pregnancies are expected to end in a live birth. The final estimates for the annual number of pregnancies in women with SLE were 449 (Carelon Research), 445 (DAPI), 50 (RHEKISS), 41 (Denmark), 32 (Finland) and 558 (France).

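### In Finland, infused anifrolumab is visible only in regional hospital records, but the cohort and counts assume national capture, so women infused elsewhere would be counted as comparators

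*Protocol*

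**What the plan says.** **Where the exposure is recorded.** Section 9.4.1.2 says of the national care register (HILMO) that "there is no data available on hospital administered medication, which is captured in the electronic medical records". The prescription registers give oral and subcutaneous biologics, while "hospital administered medication, including anifrolumab, are available from EMRs".

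**What the EMRs cover.** The same section describes the EMRs as regional. It says that "Data lag time depends on the county which needs to be selected for the studies" and, of their content, "Most of them include diagnosis, procedures, clinical notes, laboratory test results and hospital administered medication". The three largest districts are listed with about 1.7 million, 500,000 and almost 500,000 residents. No county is named as chosen for this study.

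**How Finland is treated elsewhere.** Section 9.2 names the national registries as the Finnish source. Table 8 gives Finland 100% coverage and marks anifrolumab *Available*; France, whose hospital-drug capture is also conditional, is marked *Partial* in that column. The Finnish datasets in Table 15 do not include the EMRs. In Section 9.5.1.2 the number of pregnancies is built from "Data source coverage: Proportion of the country's total population covered by the data source", with no factor for how much of the exposure is captured.

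**Who is unexposed.** Under Section 9.2.2 (STEP 2B) and Section 9.3.1, a woman on SLE standard of care with no anifrolumab record in the relevant window is unexposed. STEPs 1 to 3 set no condition on residence or EMR coverage.

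**The concern.** The cohort is drawn from one footprint (the whole country) and the infusion exposure from another (the counties whose EMRs are extracted and hold hospital medication). Where the two differ, a missing record does not mean no exposure. A woman infused in a county that is not captured satisfies STEP 2B and becomes a comparator.

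This misclassification follows place of treatment. It moves the Finnish RR towards 1, which is the unsafe direction in a study designed to rule out an RR of 2.5. Finnish results are reported separately (Section 9.7), and Section 9.7.1 pools every country for which an adjusted RR is obtained. The Finnish entries in Tables 9 to 11 also hold only if capture is complete, a condition the protocol does not state.

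**Working it through.** **1. Reproduce the plan's Finnish counts.** Inputs from Sections 9.5.1.1 and 9.5.1.2: 32 SLE pregnancies per year, 50% moderate-to-severe, 80% without confirmed teratogens, 80% of exposed pregnancies exposed in the first trimester, uptake 5% or 10%.

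- Eligible for pregnancy loss: 32 × 0.5 × 0.8 = 12.8 per year (stated 12).
- Eligible for MCM: 12.8 × 0.8 = 10.24 per year (stated 10).
- The Finnish accrual time is not stated (launch still to be confirmed). About 5.4 years fits. At 10% uptake, 12.8 × 0.10 × 5.4 = 6.9 and 10.24 × 0.10 × 5.4 = 5.5, so 7 and 6. At 5% uptake, 3.5 (3.456 before rounding) and 2.8, so 3 and 3. All match Tables 10 and 11.
- Probability of at least one exposed event: 1 − 0.8^7 = 79% for loss and 1 − 0.93^6 = 35% for MCM, as in Table 11.

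Every term is national and none allows for incomplete capture, so these counts assume a capture share of c = 1.

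**2. Let c be below 1.** The protocol gives no value, so the range 30–70% is an assumption, and uptake is taken as 10% in every county. With u the uptake:

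- exposed pregnancies seen for loss = 7c;
- truly exposed share of comparators k = u(1 − c)/(1 − uc);
- RR measured when the true RR is 2.5 = 2.5/(1 + 1.5k).

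| c | Exposed seen (loss) | k | Measured RR |
|---|---|---|---|
| 0.3 | 2.1 | 0.07/0.97 = 7.2% | 2.26 |
| 0.5 | 3.5 | 0.05/0.95 = 5.3% | 2.32 |
| 0.7 | 4.9 | 0.03/0.93 = 3.2% | 2.38 |

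For MCM the exposed count scales as 6c: 1.8, 3.0 and 4.2.

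**3. Effect on the whole study.** Finland contributes 7 of 497 exposed pregnancies for loss and 6 of 353 for MCM. At c = 0.5 the totals fall to 497 − 3.5 = 493.5 and 353 − 3 = 350. Simulating the fixed-effect inverse-variance meta-analysis of Section 9.5.1.3 for MCM at 10% uptake gives 96.1% power (1:2) and 98.3% (1:3) from the two USA sources and France, against the stated 96% and 98%. Adding Finland with 6 or with 3 exposed pregnancies leaves these at 96% and 98%.

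**4. Chance that Finland enters the pooled RR.** This needs an adjusted RR and at least one event per group. Section 9.7.1 limits the propensity score model to one fifth of the smaller group in confounders. With 7 exposed, 7/5 = 1.4, so one confounder. A Finnish adjusted RR is unlikely.

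**The case against.** A reader might infer that the stated Finnish counts cannot be reached. The documents do not support that. They do not say that only some counties will be used: the passage on county selection describes the EMRs in general, and it adds that EMR data can be linked and applied for under the same permit. The shortfall therefore cannot be computed. What stands is narrower. Complete capture is neither planned nor stated, and it is unlikely when only most EMRs hold the drug.

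A reader might also take the measured RRs of 2.26–2.38 as a property of the plan. They are illustrations. Section 9.4.1.2 says counties have their own or joint procurement agreements that decide which products are used, so uptake may differ by county, and a county that does not list anifrolumab may have few users to misclassify.

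Three further points stand in part:

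- Visibility only in EMRs applies to the infusion. Section 9.3.1 allows for a change of administration route, and a subcutaneous form would appear in the national prescription registers.
- The 100% coverage in Table 8 is correct, since Section 9.5.1.2 defines coverage as a share of the population. Only the *Available* entry is in question, and a Table 8 footnote says it rests on biologics and belimumab as a proxy.
- Section 9.9 admits that infused anifrolumab may be under-detected, with bias towards the null. That caveat is general and does not mention regional capture in Finland.

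The strongest procedural defence is that country-specific continuous-enrolment criteria are left to the SAP (footnotes to STEP 2). Their example, however, asks only for a prior healthcare contact without emigration or death, which says nothing about EMR coverage. The *Available* entry, the missing EMRs in Table 15 and the unqualified counts are in the protocol itself.

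**Conclusion.** The point holds as an internal mismatch with a real but small consequence. For the infusion, Finnish exposure is regional while the cohort, the availability entry and the counts are national, and the unexposed rule turns uncaptured users into comparators. The bias is towards 1 in the Finnish results. Its size depends on an unstated capture share and on how uptake varies by county. On the assumed 30–70% capture and uniform 10% uptake, about 2–5 exposed pregnancies for loss would be seen instead of 7, and 3–7% of Finnish comparators would be truly exposed.

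Finland is outside the sample size and power calculations, so study power does not change, and any weight in the pooled RR would be minimal. This is a worthwhile correction to make before extraction. It is not a threat to the main conclusion.

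**What to change.** - Restrict both Finnish sub-cohorts to women resident, from 16 weeks before LMP2 to the end of the exposure window (first trimester for MCM, end of pregnancy otherwise), in counties whose extracted EMR holds hospital-administered medication.
- Mark Finnish anifrolumab capture *Partial* in Table 8, with a note that it depends on the EMRs. The 100% population coverage may stand for the registers.
- Add the EMRs to the Finnish datasets in Table 15.
- State the Finnish counts in Tables 9 to 11 as conditional on EMR coverage, or scale them once the counties are known.

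The cost is one residence criterion in the Finnish extraction, a few table corrections and fewer Finnish comparators.
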